6.2 Data Security

Paper data collection forms that contain personal identifiers and health information will be kept locked in a filing cabinet in the Department of General Internal Medicine. Study variables and outcomes will be entered into an electronic database using identification numbers for the study subjects. With the exception of dates, the database will not contain personal identifiers. Only study staff will have access to the paper data collection forms and electronic database. In addition, all electronic data will be password-protected and stored on a HIPAA compliant university computer in the Department of General Internal Medicine. Any forms linking collected data with patient identifiers will be destroyed at the completion of the study (2 years following termination of patient enrollment).

6.3 Data and Safety Monitoring

A. Periodic Data Evaluation

Protocol Number:

PI Name: [name]

Protocol Title: Determining Optimal Dose of
Corticosteroids in COPD Exacerbations: A
Pilot Study

16

RESERVED FOR IRB STAMP
DO NOT MODIFY THIS SPACE

IRB Form Version v120116

Study staff responsible for data collection will review that data for potential corticosteroid adverse effects / unexpected patient outcomes and report problems to [name], [name], and [name]. Study policies involving adverse effect / death reporting to the IRB are in place and detailed above.

B. Type of Data Evaluated

Data reviewed includes predefined corticosteroid adverse effects in the data collection form and unexpected patient outcomes discovered by study staff.

C. Collection of Safety Information

Safety information is collected by study staff interviewing the patient and reviewing their chart while hospitalized, as well as phone interview and final chart review of index hospitalization and subsequent healthcare encounters at 30-day follow up.

D. Frequency Of Data Collection

Safety information is collected daily while the subject is hospitalized, starting at the point of patient recruitment. It is collected once more at the 30-day subject follow up.

E. Reviewer of Data

Study staff (co-investigators) responsible for patient recruitment/data collection/patient follow up will conduct an initial review of the data. Potential problems are reported to [name], [name], and [name] who will provide secondary review.

F. Schedule Of Review Of Cumulative Data

Cumulative data is not reviewed in this study, as it is a pilot study with a small sample size and is not powered to attain statistical significance for secondary safety outcomes.

G. Tests for Safety Data

N/A, see section F above.

H. Suspension of Research

Research will be immediately suspended if a serious, unexpected adverse effect is reported that is reasonably thought to be a direct result of the study drug and is thought to pose a risk to other study subjects beyond that of receiving standard-of-care doses of corticosteroids.

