1.0 Research Introduction

1.1 Purpose/Specific Aims

The goal of the study is to determine whether a high-dose corticosteroid regimen in patients admitted to the hospital with COPD exacerbations is associated with better clinical outcomes and at acceptable risk of adverse effects compared to a low-dose corticosteroid regimen. The study population includes patients ≥ 40 years-old with a ≥ 10 pack-years smoking history and a diagnosis of COPD, emphysema, or chronic bronchitis who present to the emergency room with increased dyspnea, increased sputum, or increased cough that requires admission to the hospital. We will perform a prospective, randomized, double-blinded study to determine if a high-dose corticosteroid regimen, which is already in use in clinical practice, decreases treatment failure compared to a low-dose corticosteroid regimen that is based on national consensus guidelines.

A. Objectives

Primary Aim: To determine if a high-dose corticosteroid regimen is associated with decreased rates of treatment failure compared to a low-dose corticosteroid regimen.

Secondary Aims:

- a) To determine if a high-dose corticosteroid regimen is associated with a reduced length of stay.
- b) To determine if a high-dose corticosteroid regimen is associated with better quality of life scores.

Tertiary Aim: To determine if a high-dose corticosteroid regimen is associated with an increased risk of short-term adverse effects.

B. Hypotheses / Research Question(s)

Protocol Number:

PI Name: [name]

Protocol Title: Determining Optimal Dose of
Corticosteroids in COPD Exacerbations: A
Pilot Study

3

RESERVED FOR IRB STAMP
DO NOT MODIFY THIS SPACE

IRB Form Version v120116

Our hypothesis is that high-dose corticosteroids are associated with a decreased rate of treatment failure, shorter length of hospital stay, and improved quality of life with similar risk of adverse effects.

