1.3 Research Design and Methods

We will perform a pilot study evaluating two commonly used doses of corticosteroids in the treatment of acute exacerbation of COPD. The study design is a randomized, double-blinded, prospective interventional trial. Our research staff will recruit, consent, and enroll patients admitted to the hospital with a diagnosis of COPD exacerbation. We will create randomization tables that will be provided to the research pharmacist. The research pharmacist will be telephoned, and they will randomly assign the patient to a low-dose or high-dose corticosteroid regimen. Medication will be prepared by a research pharmacist to maintain blinding. For in-hospital intravenous medication, the research pharmacist will provide to the nurses a container with the patient's name and medication without the dose. For oral medication, the pills will be inserted into a capsule and provided to nurses for in-hospital administration. At the time of discharge, a container filled with the remaining oral medication will be provided to the patient. Subjects receiving intravenous corticosteroid may be discharged to a nursing home before completion of the IV component of the regimen. Their regimen will be converted to oral equivalents, and a container will be provided to the nursing home. Copies of the patient brochure, signed consent, and written discharge instructions will also be provided. All data will be collected by our research staff via chart review of index and subsequent hospitalizations within the 30-day follow up period, as well as a phone interview with the patient at 30-days. The Clinical COPD Questionnaire will be administered during the phone interview. A patient is considered lost to follow-up if the data collection is not collected within 14 days after the 30-day follow-up date. In the event that we are unable to contact the patient, we will telephone the participant's personal medical doctor to confirm the patient's status. If necessary, we will obtain medical records for any outpatient physician visits made during the 30-day follow up period.

- i. Primary Outcome: The composite of treatment failure defined as death, intubation, re-admission for COPD exacerbation, or intensification of therapy (increased steroid use, change of antibiotic therapy) within a 30-day follow-up period.

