Subjects will interact with a limited number of study staff, primarily during the initial recruitment/inpatient follow-up period. Any privacy interests will be honored by study staff.

I. Research Team Access To Subject Data

Study participants will be asked to sign a Release of Medical Record form, allowing the research team to access medical information from all subsequent hospitalizations and outpatient physician visits within the 30-day follow up period.

4.10 Secondary Data – Records/Chart Reviews/Databases/Tissue Banks/etc.

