6.4 Reporting Results

A. Sharing of Results with Subjects

Results will not be shared with study subjects since no data is collected that is not ordered by the patient's treating physician.

B. Individual Results

N/A, see section A above.

C. Aggregate Results

Aggregate results will not be available for an extended period of time following study completion and will not be shared on an individual basis with study subjects. The study results will be published in a scientific journal for public consumption.

D. Professional Reporting

The study results will be published in a scientific journal for public consumption.

E. ClinicalTrials.Gov Registration And Data Reporting

The study is registered on ClinicalTrials.gov.

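### After discharge, adverse effects are sought only once, at day 30, so detection of the harm composite depends on length of stay, which treatment may change

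*Combined protocol and SAP*

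**What the plan says.** **Frequency.** Section 6.3.D states "Safety information is collected daily while the subject is hospitalized, starting at the point of patient recruitment" and then "It is collected once more at the 30-day subject follow up". Section 4.6 likewise places the daily staff conversation in the hospital stay only. Section 1.10 allows a further 14 days to obtain follow-up, so the contact can fall as late as day 44 (30 + 14).

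**Sources at day 30.** Section 6.3.C adds to the in-hospital review "as well as phone interview and final chart review of index hospitalization and subsequent healthcare encounters at 30-day follow up". Under section 4.9.I a signed release lets the team "access medical information from all subsequent hospitalizations and outpatient physician visits within the 30-day follow up period". Section 1.3 makes the outpatient part conditional: "If necessary, we will obtain medical records for any outpatient physician visits made during the 30-day follow up period". Section 1.9 puts questions on steroid adverse effects into the telephone interview.

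**Treatment.** Section 1.7 gives both arms the same number of dosing days and foresees discharge before day 4. Under section 1.3 the rest of the course goes home with the patient ("At the time of discharge, a container filled" with the remaining oral doses).

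**Outcome and analysis.** The tertiary composite (sections 1.3 and 1.6) counts six named effects, and only when they led to a consult, an invasive procedure or a new treatment. It has no stated time window; the primary outcome has one of 30 days. Section 6.1.A compares event rates by assigned arm with chi-square tests.

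**Hypothesis.** Section 1.1.B expects, for high dose, "shorter length of hospital stay, and improved quality of life with similar risk of adverse effects".

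**The concern.** A patient in hospital is asked and chart-reviewed about harms every day. A patient at home on the same day of the same course is asked once, weeks later. The switch from one regime to the other happens at discharge, and time to discharge is an outcome the treatment may affect. Randomisation therefore does not guarantee equal detection in the two arms.

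Chart review recovers only what became a record. A raised glucose or blood pressure that nobody measures at home prompts no consult and no treatment, so it never meets the composite's definition. The same value in hospital is more likely to be measured and acted on. Section 4.9 says minor effects such as hyperglycaemia usually last no longer than treatment, and it limits psychiatric effects in the same way. The only post-discharge question comes about 20 days after the last dose (30 − 10), when such effects are expected to have gone.

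Two things are at stake. If high dose does shorten stay, the distortion favours the hypothesised finding of similar risk. Also, section 1.5 says the pilot exists to estimate outcome rates for a larger trial. Under-detected harm rates would be carried into that trial, and the same schedule at larger size would shrink the sampling error but keep the bias.

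**Working it through.** **Course length.** Adding the steps in section 1.7 gives 3 + 4 + 1 + 1 + 1 = 10 days in each arm, which agrees with the 10-day period in section 1.2.

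**Model.** The documents give no harm rates, expected stays or detection rates, so the following are assumptions:
- L = dosing days spent in hospital
- s = detection after discharge relative to detection in hospital (in hospital = 1)
- events spread evenly over the 10 dosing days

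Detected share in an arm = [L + s(10 − L)] / 10. Observed ratio = true ratio × (share, high) / (share, low).

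**Results for a true ratio of 1.50:**

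| Stay, high vs low (days) | s | Share, high | Share, low | Factor | Observed ratio |
|---|---|---|---|---|---|
| 4 vs 5 | 0.5 | 0.70 | 0.75 | 0.933 | 1.40 |
| 4 vs 5 | 0.7 | 0.82 | 0.85 | 0.965 | 1.45 |
| 4 vs 5 | 0.9 | 0.94 | 0.95 | 0.989 | 1.48 |
| 4 vs 6 | 0.5 | 0.70 | 0.80 | 0.875 | 1.31 |
| 4 vs 6 | 0.9 | 0.94 | 0.96 | 0.979 | 1.47 |
| 6 vs 5 | 0.5 | 0.80 | 0.75 | 1.067 | 1.60 |
| 6 vs 5 | 0.9 | 0.96 | 0.95 | 1.011 | 1.52 |
| any | 1.0 | 1.00 | 1.00 | 1.000 | 1.50 |

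**Uneven timing.** Suppose 60% of events fall in days 1–3, 30% in days 4–7 and 10% in days 8–10. With stays of 4 vs 5 and s = 0.5:
- high: 0.675 + 0.5 × 0.325 = 0.8375
- low: 0.75 + 0.5 × 0.25 = 0.875
- factor 0.957, observed ratio 1.44

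**Absolute scale.** Assume true risks of 30% (high) and 20% (low), a difference of 10 points.
- Stays 4 vs 5, s = 0.5: 30 × 0.70 = 21.0% and 20 × 0.75 = 15.0%, difference 6.0 points.
- Same stays, s = 0.9: 28.2% and 19.0%, difference 9.2 points.
- Equal stays 5 vs 5, s = 0.5: 22.5% and 15.0%. The ratio stays at 1.50, but the difference falls to 7.5 points and a quarter of the events are missed in both arms.

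**Sampling error for comparison.** With 125 patients split equally (62.5 per arm; equal allocation is assumed), the 95% half-width for the risk difference is 1.96 × √(0.30 × 0.70/62.5 + 0.20 × 0.80/62.5) = 15.1 points. Power at two-sided 0.05 is about 25%; 80% would need about 294 per arm.

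**The case against.** The strongest reply is that day-30 collection is more than a telephone question. It includes chart review of later care, backed by a signed release, and the composite counts only effects that led to some action, many of which leave a record. This stands, and it is why values of s near 0 are unrealistic. It does not close the gap: outpatient records are sought only when judged necessary, and an effect nobody measured at home leaves nothing to retrieve.

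Four stronger readings are tempting, and the documents do not support them.
- *Post-discharge harms rest on recall alone.* Section 6.3.C says otherwise.
- *Nothing is measured beyond what the physician orders.* Section 6.4.A does say "no data is collected that is not ordered by" the treating physician, but there it explains why results are not returned to patients. Staff collect other data, such as the quality-of-life questionnaire and the endpoint questions. The data collection form holding the predefined adverse effects is not among the documents, so what it schedules cannot be judged.
- *A true ratio of 1.50 could vanish.* That needs s = 0 and a two-day difference in stay (4/6 = 0.667; 1.50 × 0.667 = 1.00), so that nothing is ever found after discharge.
- *The bias surely favours high dose.* The cohort described in section 1.2 found shorter stay with low dose, and that direction would exaggerate high-dose harm. An adverse effect that itself prolongs stay would also raise detection in the affected arm.

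It can also be said that this is a tertiary outcome in a pilot that disclaims power, and that 15 points of sampling error exceed the 0.8 to 4.0 points lost in the 4 vs 5 day examples. That is right as to this trial's own test. It does not answer the point about the rates passed on to a larger trial.

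**Conclusion.** The concern holds in a limited form. The documents establish that harm detection is daily in hospital and single after discharge, that part of the course may be taken at home without contact, and that the planned comparison ignores the difference. Detection of the composite therefore depends on a post-randomisation outcome.

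The direction is conditional on which arm stays longer. The size is probably modest: under the one-day difference shown, the ratio moves by about 1 to 7% for s between 0.9 and 0.5. These figures rest on assumed stays, assumed detection and mostly even event timing; nothing in the documents fixes them. If s = 1 there is no bias. It would go too far to infer that the tertiary aim cannot be answered. What is not supported is a conclusion of similar harm drawn from the 30-day composite alone when stay differs between arms. Loss of events also lowers the pilot's harm rates even when stays are equal.

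**What to change.** 1. **Sections 6.3.D and 1.9:** put the existing adverse-effect questions to every patient once at the end of study drug, about day 11 from randomisation, whether or not discharged.
2. **Section 6.1.A:** report the harm composite over the common window from randomisation to that contact, and over 30 days, with in-hospital and post-discharge events shown separately in each arm.
3. **Section 6.1.A:** state that similar harm will not be claimed from the 30-day composite alone if length of stay differs between arms.

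The cost is one short call per discharged patient, by staff who already make the day-30 call, plus a few lines of analysis text. No treatment changes.

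The call reduces the dependence on stay but does not abolish it, since in-hospital days are still reviewed daily and unmeasured effects at home stay unmeasured. It does nothing for precision. A window confined to days 1–3 would need no new contact but is a poor main remedy: section 1.7 foresees discharge before day 4, and such a window drops seven of the ten dosing days.

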6.4 Reporting Results

A. Sharing of Results with Subjects

Results will not be shared with study subjects since no data is collected that is not ordered by the patient's treating physician.

B. Individual Results

N/A, see section A above.

C. Aggregate Results

Aggregate results will not be available for an extended period of time following study completion and will not be shared on an individual basis with study subjects. The study results will be published in a scientific journal for public consumption.

D. Professional Reporting

The study results will be published in a scientific journal for public consumption.

E. ClinicalTrials.Gov Registration And Data Reporting

The study is registered on ClinicalTrials.gov.

7.0 Data and/or Specimen Banking

Protocol Number:

PI Name: [name]

Protocol Title: Determining Optimal Dose of
Corticosteroids in COPD Exacerbations: A
Pilot Study

17

RESERVED FOR IRB STAMP
DO NOT MODIFY THIS SPACE

IRB Form Version v120116

N/A

8.0 Other Approvals/Authorizations

N/A

